5.4.8 MRI Safety Data

Brain MRI safety finding (may include T1, fluid-attenuated inversion recovery, gradient echo) or other modalities and sequences (to be detailed in Imaging/MRI manual) are assessed at Screening visit, Week 24 and 52 visits.

The MRI safety result is classified as normal or abnormal. Shift table from normal or unknown MRI at baseline to abnormal post-baseline MRI will be summarized. The worst post-baseline record of each subject is selected. A listing of details for abnormal brain MRI findings will also be presented.

CONFIDENTIAL

The information contained herein may not be used, disclosed, or published without the written consent of Biogen MA Inc.

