With an estimated sample size of 100 subjects dosed per arm in the 1250 mg and 3500 mg arms, the study has 80% probability of detecting AEs with a rate of 1.6% or greater in these 2 arms, and a 90% probability of detecting AEs occurring with a rate of 2.3% or greater.

Table 4.1: Estimated Sample Size Per Group (Planned)

	Treatment Group				Total
	Placebo	BIIB054 250 mg	BIIB054 1250 mg	BIIB054 3500 mg	
Cohort					
Cohort A	6	6	6	6	24
Cohort B	82	41	82	82	287
Total	88	47	88	88	311

Table 4.2: Estimated Sample Size Per Group Based on Actual Enrollment (Before Drop-Outs)

	Treatment Group				Total
	Placebo	BIIB054 250 mg	BIIB054 1250 mg	BIIB054 3500 mg	
Cohort					
Cohort A	8	7	7	7	29
Cohort B	93	47	94	94	328
Total	101	54	101	101	357

Table 4.3: Estimated Sample Size Per Group Based on Actual Enrollment (After Adjusting for 10% Drop-Out At Week 52)

	Treatment Group				Total
	Placebo	BIIB054 250 mg	BIIB054 1250 mg	BIIB054 3500 mg	
Cohort					
Cohort A	7	6	6	6	25
Cohort B	84	42	84	84	294
Total	91	48	90	90	319

[figure not shown]
Table 1: Estimated Sample Size Per Group Based on Actual Enrollment (After Adjusting for 15% Drop-Out At Week 72)

	Treatment Group				Total
	Placebo	BIIB054 250 mg	BIIB054 1250 mg	BIIB054 3500 mg	
Cohort					
Cohort A	7	6	6	6	25
Cohort B	79	40	80	80	279
Total	86	46	86	86	304

CONFIDENTIAL

The information contained herein may not be used, disclosed, or published without the written consent of Biogen MA Inc.

Figure 4.1: Candidate Models for Dose-Response

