5.2.2 Demographics and Baseline Characteristics

Demographic data, including age (in years), age category (40-50, 51-60, 61-70, 71-80 years), gender, race, ethnicity, height, weight, body mass index (BMI), country (region) and year of education at baseline will be summarized by treatment groups and overall.

Baseline PD history will be summarized by treatment groups and overall, using descriptive statistics. Time since onset of PD symptoms (in years), time since PD diagnosis (in years), subtype of PD (PIGD, TD or indeterminate), side predominately affected at disease onset, symptoms presented at PD diagnosis and immediate family with a history of Parkinson's Disease will be summarized. MDS-UPDRS total and subtotal scores, PIGD, TD, and LE subscore, Hoehn and Yahr stage, [REDACTED] will be summarized. DaT/SPECT imaging outcomes, [REDACTED] outcomes will also be summarized. Baseline MDS-UPDRS score is defined as the Day 1 visit, if Day 1 visit score is not available, screening visit will be used. Baseline PD history data will be listed.

Number (%) of subjects with any PD treatment history will be summarized by treatment groups and overall. Total duration of previous therapies and reason for stopping therapies will be summarized. Number (%) of subjects who had taken MAO-B inhibitors, Dopamine Agonist, Levodopa and other PD medications will be displayed by treatment groups and overall. A listing of PD treatment history will be generated.

Medical history will be coded using the Medical Dictionary for Regulatory Activities (MedDRA). The number (%) of subjects with history (including both ongoing and not ongoing medical conditions) will be summarized by system organ class and preferred term, and by preferred term only. A listing of medical history will be generated.

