4.5.8 MRI Safety Data

Brain MRI safety findings are assessed at Screening visit, Week 24, 52, 96, 148 and 4 weeks after last dose/ET visits.

The MRI safety result is classified as normal or abnormal. Shift table from normal or unknown MRI at baseline to abnormal post-baseline MRI will be summarized in the active treatment (placebo-controlled and DBE) period. The worst post-baseline record of each subject is selected. A listing of details for abnormal brain MRI findings will be presented for placebo-controlled and DBE period.

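### The only defined MRI safety table leaves out new or worsened findings in subjects whose baseline MRI was already abnormal; add a by-arm count that does not depend on baseline class

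*SAP*

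**What the plan says.** Year 1 SAP 5.4.8 schedules safety MRI at screening, Week 24 and Week 52. It sets a two-level result: "The MRI safety result is classified as normal or abnormal". The tabulation rule is "Shift table from normal or unknown MRI at baseline to abnormal post-baseline MRI will be summarized", and for the record used, "The worst post-baseline record of each subject is selected". No denominator is given. The section ends with a listing: "A listing of details for abnormal brain MRI findings will also be presented".

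The extension SAP, section 4.5.8, adds scans at Week 96, Week 148 and four weeks after the last dose or at early termination. It keeps the same scale and the same worst-record rule, and also plans a listing. Its table rule is "Shift table from normal or unknown MRI at baseline to abnormal post-baseline MRI will be summarized in the active treatment (placebo-controlled and DBE) period".

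Section 6 of the Year 1 SAP and section 4.10 of the extension SAP name a summary of MRI safety findings among the key safety outputs at Week 72. Neither defines its format.

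**The concern.** Repeated safety MRI on treatment is there to show what has changed since the subject's own baseline scan. A table that admits only subjects with a normal or unknown baseline cannot show change in the rest. Treating normal or unknown as the starting group itself implies that abnormal baselines are expected.

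The part of each arm that is left out is not described, and it may differ between groups. In the extension, the general baseline rule in section 4.1 gives delayed-start subjects the last value before their first extension dose, while early-start subjects keep the Year 1 baseline. A delayed-start subject who became abnormal during the placebo year therefore drops out of the numerator. An early-start subject who became abnormal over the same year is counted as a shift.

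At stake is how easily a dose-related MRI pattern could be seen in a by-arm comparison, including at Week 72.

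**Working it through.** **1. The possible paths through the table.** With a two-level post-baseline result and baseline normal, unknown or abnormal:

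| Baseline | Worst post-baseline | In the planned shift table? |
|---|---|---|
| Normal | Abnormal | Yes |
| Unknown | Abnormal | Yes |
| Abnormal | Abnormal, nothing new | No |
| Abnormal | Abnormal, new or worsened finding | No |

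The last two rows carry the same code. Even a full cross-tabulation of baseline by post-baseline class would merge them. The remedy therefore has to use the finding details, not a wider shift table.

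**2. How other safety domains in the Year 1 SAP are handled.**

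- *Laboratory (5.4.3.2):* shift tables with stated at-risk denominators, plus a count of potentially clinically significant values in anyone with a post-baseline evaluation, whatever the baseline.
- *Vital signs (5.4.4):* counts against fixed limits and against change from baseline.
- *ECG (5.4.5):* a shift table, plus counts of QTcF outliers.
- *Physical and neurological examination (5.4.6):* abnormal findings go to the adverse event summary by rule.
- *MRI (5.4.8):* one shift table and a listing, with no second tabulated route and no sentence sending findings to adverse events.

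**3. Illustration of size.** The documents give no share of abnormal baseline scans, so the shares below are assumptions. The only detection figure in the plan is in section 4 of the Year 1 SAP, for 100 subjects per arm: "80% probability of detecting AEs with a rate of 1.6% or greater in these 2 arms", and 90% at a rate of 2.3%. It concerns adverse events, not MRI.

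Formula: P(at least one) = 1 − (1 − p)^n.

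The plan's own figures first, with n = 100:

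- p = 0.016: 1 − 0.984^100 = 0.801, which reproduces 80%.
- p = 0.023: 1 − 0.977^100 = 0.902, which reproduces 90%.

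The same formula with n reduced to the subjects who can enter the shift table:

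| Assumed share abnormal at baseline | n at risk | p = 1.6% | p = 2.3% |
|---|---|---|---|
| 0% | 100 | 0.801 | 0.902 |
| 10% | 90 | 0.766 | 0.877 |
| 20% | 80 | 0.725 | 0.845 |
| 30% | 70 | 0.677 | 0.804 |
| 40% | 60 | 0.620 | 0.752 |
| 50% | 50 | 0.554 | 0.688 |

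These are chances of at least one case in the MRI shift table alone. They assume the same rate of new findings whatever the baseline class. They ignore what the listing and the adverse event tables would show.

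**The case against.** **Other routes exist.** A reader might infer that a new lesion in a baseline-abnormal subject is counted nowhere. The documents do not support that. The listing in 5.4.8 is not limited to subjects with a normal baseline. Section 5.4.2 records every adverse event from first dose to end of study, treats both new and worsened events as treatment-emergent, and tabulates them by treatment group. A finding reported as an adverse event is counted by arm whatever the baseline scan. What remains is that this route is conditional: the SAP does not say that MRI findings are reported as adverse events. The listing gives no by-arm count and does not call for comparison with the baseline scan.

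**The worst-record rule.** It might seem empty on a two-level scale, but it is not. With more than one post-baseline scan, it makes an abnormal Week 24 scan count even if Week 52 is normal. It cannot rank findings, which is a different matter.

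**Unknown baselines.** Counting unknown to abnormal as a shift may look like counting old findings as new. It is the SAP's own convention for laboratory data and ECG, and it errs toward showing a signal.

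**Extension baseline.** A reader might think a baseline for delayed-start subjects still has to be set. Section 4.1 of the extension SAP already sets it.

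**Size and unseen documents.** The plan's detection figures concern adverse events, whose tables are not restricted by baseline MRI, so their power is not reduced. The age bands in 5.2.2, from 40 to 80 years, say nothing about the share of abnormal scans. Section 5.4.8 refers to an imaging manual for scan modalities and sequences. The manual or the protocol may limit baseline abnormalities or require adverse event reporting, and either would shrink the gap. This objection stands in full against any firm statement of size.

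**Week 72.** It is tempting to assume that the Week 72 summary is this shift table. Its format is undefined, so that is only an inference.

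**Conclusion.** The point holds as a limited gap in tabulation. The one MRI safety table defined in each SAP omits new or worsened findings in subjects with an abnormal baseline scan, and nothing else drawn from the MRI data counts them by treatment group. This follows from the text and does not depend on the share of abnormal baselines, provided there are some.

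The practical size is unknown. It depends on that share, on the rate of new findings in those subjects, and on how many are reported as adverse events. The documents give none of these. The table of detection probabilities shows the direction only. The documents do not show that a signal would be missed, so this is a worthwhile low-cost improvement and not a failure of the safety plan.

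**What to change.** Keep the shift table. In Year 1 SAP 5.4.8 and extension SAP 4.5.8, add a table by treatment group of subjects with at least one new or worsened MRI finding compared with their own baseline scan, by type of finding and whatever the baseline class. State the denominator as subjects with a baseline scan and at least one post-baseline scan. Subjects without a baseline scan stay visible in the existing shift table.

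Build the table from the finding details already collected for the listing. For delayed-start subjects, cite the baseline already defined in section 4.1 of the extension SAP. Name the new table as part of the Week 72 summary of MRI safety findings, whose content is now open.

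The cost is one additional table per SAP and some coding of the finding descriptions. No new scans or assessments are needed.

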5.5 Pharmacodynamic -Imaging Analysis

5.5.1 Type of imaging techniques and imaging outcomes

There are three types of imaging techniques used in the study:

(1) DaT/SPECT imaging,

(2) [REDACTED]

[REDACTED]

(3) [REDACTED]

DaT/SPECT imaging assesses the biological effects of BIIB054 on brain dopamine neurons and nerve terminals. DaT-associated outcome measures include the estimates of anterior and posterior putamen, caudate, as well as total striatum striatal binding ratio (SBR), a measure that compares signal intensity in the region of interest to that in the occipital cortex, a region relatively devoid of dopamine nerve terminals. Measurements are obtained both ipsilateral and contralateral to the side of worst motor symptoms, anterior, posterior as well as combining both sides.

[REDACTED]

[REDACTED]

[REDACTED]

[REDACTED]

[REDACTED]

5.5.2 Analysis population

All pharmacodynamic imaging endpoints will be evaluated based on the Pharmacodynamics population as defined in Section 5.1.2.

5.5.3 Baseline value

Baseline value is defined as the latest data collected at any time prior to the first dose, or if collected only after dosing the earliest data on the first dose date, given the data is collected within 1 week after first dose date.

5.5.4 Outlier of percent change from baseline

If the percent change from baseline in a post-baseline value of a DaT/SPECT SBR measure is greater than 50% or less than -50%, the post-baseline value of the DaT/SPECT measures is considered as physiologically implausible, and therefore will be excluded in the analysis.

5.5.5 Analysis methods

The estimand of the primary analysis for imaging outcome measure is the mean difference of the change from baseline in the imaging measure at Week 52 between treatment groups in the

	Statistical Analysis Plan Placebo-Controlled Period	V1.0
---	---	-------------

pharmacodynamics population regardless of whether start of PD medication had occurred or not. Specifically, the estimand takes the following into consideration:

- A. Population: pharmacodynamics population as defined in Section 5.1.2;
- B. Variable: change from baseline to Week 52 in the imaging measure;
- C. Intercurrent events: regardless of whether start of PD medication had occurred or not;
- D. Population-level summary: difference in variable means between each active treatment and placebo group

A set of DaT/SPECT measures and [REDACTED] have been selected for the statistical analyses based on literature review and clinical inputs before the DBL. Please see Appendix VI for the listed measures.

Data collected after subjects who have begun taking PD medication will be included in the primary analysis. Change and percent change from baseline will be summarized by visit and treatment groups using descriptive statistics. Change or percent change from baseline in the imaging measures will be analyzed using the mixed model for repeated measures (MMRM), which includes the fixed effect of the treatment group (categorical), time (categorical), interaction between treatment group and time, region (categorical), baseline imaging values (continuous), baseline imaging values by time interaction, baseline MDS-UPDRS I+II+III total score (continuous) and baseline MDS-UPDRS I+II+III total score by time interaction. An unstructured covariance matrix will be used to model the within-subject variance-covariance errors. If the unstructured covariance structure matrix results in a lack of convergence, the heterogeneous Toeplitz covariance structure followed by the heterogeneous first-order autoregressive covariance structure will be used. The Kenward-Roger approximation will be used to estimate the denominator degrees of freedom. Least square means (LSmeans) of each treatment group as well as treatment difference between each BIIB054 groups and placebo will be displayed with 95% CI and p-value at Week 52. If the distribution of the outcome is highly skewed, p-value will be generated from the MMRM model based on the rank data. In the primary analysis, missing data are assumed to be missing at random (Rubin 1976), and the PD medication is assumed to have minimal impact on the imaging measures.

The same MCP-MOD method as used in the primary analyses of MDS-UPDRS I+II+III may be used to assess and model dose-response relationship of the imaging outcomes.

5.5.6 Sensitivity analysis

A sensitivity analysis will be performed using the same MMRM model in the primary analysis, but by excluding DaT/SPECT values that are collected after subjects starting PD medications.

The sensitivity analysis will be performed only for the key DaT/SPECT measures as specified in the Appendix VI.

CONFIDENTIAL

The information contained herein may not be used, disclosed, or published without the written consent of Biogen MA Inc.

5.5.7 Correlation analysis

Spearman's correlation of change from baseline to Week 52 will be computed for the following imaging and MDS-UPDRS parameters. For the pairs with MDS-UPDRS III, I+II+III and EP-RPS correlation will be computed respectively by including and excluding data after PD medication. For the other pairs, correlation will be computed by including the data after PD medication only.

- DaT-SPECT Striatum total SBR (25. STR_SBR) x MDS-UPDRS III
- DaT-SPECT Striatum total SBR (25. STR_SBR) x MDS-UPDRS I+II+III
- DaT-SPECT Striatum total SBR (25. STR_SBR) x Early Parkinson's Regional Progression Score (EP-RPS)
- DaT-SPECT Striatum total SBR (25. STR_SBR) x structural MRI Striatum total volume (13. STR_VOL)
- DaT-SPECT Striatum total SBR (25. STR_SBR) x SNc total volume via GRE (23. GRE_NM_VOL)
- DaT-SPECT Striatum total SBR (25. STR_SBR) x SNc total intensity ref 4 via GRE (98. GRE_NM_NMSIG_R4)
- NM-MRI SNc total volume via GRE (23. GRE_NM_VOL) x NM-MRI SNc total volume via TSE (9. TSE_NM_VOL)
- NM-MRI SNc total intensity ref 4 via GRE (98. GRE_NM_NMSIG_R4) x NM-MRI SNc total intensity ref 4 via TSE (37. TSE_NM_NMSIG_R4)

[Redacted]

[Redacted]

[Redacted]

[Redacted]

[Redacted]

[Redacted]

[Redacted]

[Redacted]

CONFIDENTIAL

The information contained herein may not be used, disclosed, or published without the written consent of Biogen MA Inc.

[REDACTED]

[REDACTED]

[REDACTED]

[REDACTED]

[REDACTED]

[REDACTED]

5.7 Pharmacokinetics Analysis

The PK analysis population as defined in Section 5.1.2 will be used for the description of the concentration-time profiles and for the estimation of PK parameters.

A serum drug concentration that is deemed inconsistent with dosing (very low or very high) will be excluded from the analysis if no apparent explanation exists. Concentration observations may also be removed from the data set if corresponding dosing or sampling times are missing or cannot be imputed. Concentration data with below limit of quantification value will be excluded. All exclusions of data points or subjects from the analysis will be appropriately documented.

In addition, a detailed listing of sampling time (actual and nominal) and corresponding concentration at each time point for all subjects in the PK population will be provided. Presence of anti-BIIB054 antibody will also be listed and summarized. Additional listings may be generated as deemed necessary.

5.7.1 PK Concentration Profile

Descriptive statistics (N, arithmetic mean, standard deviation, geometric mean, CV, median, minimum, maximum, 25th and 75th percentiles) will be used to summarize concentration of BIIB054 in serum and [REDACTED] by visit and treatment groups. [REDACTED].

Mean serum concentrations of BIIB054 versus time will be plotted by treatment group on both a linear and a logarithmic scale for Cohort A (doses 1 and 3 only). Dose proportionality will be assessed for Cohort A (doses 1 and 3 only) as deemed appropriate.

Additional listings or plots may be generated as deemed necessary.

5.7.2 Serum PK Parameters

All listed PK parameters below will be computed by non-compartmental methods, as data permits, from serum concentration-time data for cohort A. For cohort B, only C_{trough} will be reported, due to sparse PK collection.

Parameter	Definition/Calculation
C_{max}	Observed maximum concentration
C_{trough}	Observed concentration at the end of the dosing interval
T_{max}	Time to reach maximum concentration
AUC_{tau}	area under the concentration-time curve within a dosing interval tau
Accumulation ratio	Using C_{max} , C_{trough} , and AUC_{tau}

Individual subject PK parameter data will be listed. Descriptive statistics (N, mean, standard deviation, geometric mean, CV, median, minimum, maximum, 25th and 75th percentiles) will be used to summarize the PK parameters.

Population PK analysis will be conducted to estimate BIIB054 population PK parameters and to identify potential covariates (e.g., demographics, body weight, anti-BIIB054 mAb etc.) on the variability of BIIB054 PK. In addition, an exposure-response (ER) analysis will be conducted to detect any ER relationship trend and potential covariate using any primary or secondary endpoint and BIIB054 exposure metrics as deemed appropriate. Other tables and figures based on the population PK and ER analyses will be generated by Clinical Pharmacology and Pharmacometrics (CPP) team and will be included in a separate report from CPP.

5.8 Immunogenicity Analysis

5.8.1 Analysis Methods for Immunogenicity Data

Immunogenicity population as defined in Section 5.1.2 will be used to analyze immunogenicity data.

CONFIDENTIAL

The information contained herein may not be used, disclosed, or published without the written consent of Biogen MA Inc.

For immunogenicity, baseline value is defined as the latest data collected at any time prior to the first dose, or if collected only after dosing the earliest data on the first dose date. More specifically, if samples are only available prior to the first dose, or samples are available both prior to first dose date and on the first dose date, baseline is the latest sample prior to the first dose date. However, if samples are only available on the first dose date but not prior to the first date, baseline is the earliest sample on the first dose date.

A study subject will be given “antibody positive” status if they have at least one confirmed positive sample result at any time during the treatment or post-treatment evaluation periods. A study subject will be given “antibody negative” status if all evaluated antibody sample results are antibody negative.

Anti-BIIB054 antibody responses in antibody-positive subjects are defined as treatment emergent if a subject is:

- ADA-negative at baseline and ADA-positive post-baseline, or
- ADA-positive at baseline and had a greater than 2-fold increase in antibody titer post-baseline.

Summary table of the number and percentage of treatment-emergent anti- BIIB054-positive and -negative antibody events by visit will be displayed for each active treatment groups. A listing of all anti- BIIB054 antibody results will also be provided.

6 INTERIM ANALYSIS

Safety and PK data only will be reviewed by the IDMC after subjects in Cohort A have completed Week 12 Visit assessments, and before dosing any subjects in Cohort B.

After subjects in Cohort A complete the Week 24 Visit, [REDACTED], all available serum PK, [REDACTED] from Cohort A will be analyzed by a statistical/PK team independent of the study. The grouped level summary statistics will be reviewed only by a limited number of individuals at Biogen who are not involved in the management of the subjects or subject-level data for the study. No changes to the study design are expected based on this review.

For the purpose of planning for future studies, an administrative interim analysis may be performed when approximately 60% of the subjects have completed the Week 52 Visit. A small unblinded team from Biogen, separate from the study management team, will have access to the unblinded interim analysis results. As of the finalization of protocol Version 8 and all subjects have completed Week 52 visits, this analyses was not conducted

A full analysis of the 1-year data will be performed after all subjects have completed the Week 52 Visit. A small unblinded team from Biogen, separate from the study management team, will have access to the unblinded 1-year analysis results. All efficacy endpoints will be analyzed at the Week 52 analyses. All available safety data will also be summarized.

An interim analysis when all subjects have completed the Week 72 Visit is planned to be conducted. A small unblinded team from Biogen, separate from the study management team, will have access to the unblinded interim analysis results. All efficacy endpoints and available [REDACTED] will be analyzed at the Week 72 analyses. Selected key safety data (e.g. summary of AE and SAE, summary of MRI safety findings and incidence of anti-drug

CONFIDENTIAL

The information contained herein may not be used, disclosed, or published without the written consent of Biogen MA Inc.

antibodies) will be summarized, as this is only a snapshot of the safety profile at the time of the Week 72 interim analysis, and the comprehensive safety profile will be presented at the End of Study

A multiple comparison adjustment method will be applied to control the overall type I error at 0.05 in the study, due to the primary endpoint of change from baseline in MDS-UPDRS total score being analyzed at Week 52 and Week 72, and superiority against placebo is considered reached in the study if statistically significant result is achieved at either timepoint at the respective adjusted alpha-level.

An improved fall-back procedure will be used to control the overall type I error at 0.05 level due to multiple-testing. An alpha of 0.04 will be allocated to the Week 52 primary endpoint analyses and an alpha of 0.01 will be allocated to the Week 72 primary endpoint analysis.

- If the Week 52 analysis is statistically significant at the 0.04 level (i.e. p-value ≤ 0.04), the alpha of 0.04 will be transferred (recycled) to the Week 72 analysis, and Week 72 will have alpha=0.05.
- If the Week 52 analysis is not statistically significant at the 0.04 level, alpha of 0.01 will be used for the Week 72 analysis. Statistical significance is considered achieved if the p-value is ≤ 0.01 at Week 72.
- If statistical significance is achieved at the Week 72, in either scenarios above, then the alpha of 0.01 will be transferred (recycled) back to Week 52, and the Week 52 primary analysis will be re-evaluated for statistical significance at the 0.05 level. This will only change the conclusion of the Week 52 results if the initial p-value is greater than 0.04 and ≤ 0.05 .

No additional multiplicity adjustments will be made for secondary or [REDACTED] endpoint analyses.

A blinded sample size re-estimation may be conducted when approximately 10% of subjects have completed the Week 52 Visit or approximately 1 month before enrollment is projected to be completed, whichever is earlier (description of method is below). The study sample size may be increased based on this blinded data review. There may be small adjustments to the percentage depending on actual enrollment rate. As of the finalization of protocol Version 8 (Aug 2020), all subjects have completed Week 52 visits, this analysis was not conducted.

Blind sample size re-estimation

The sample size for this study may be reassessed in a blinded manner in a cutoff date of February 2020, by which time approximately 78/311 (25%) of subjects will complete the Week 52 visit.

The standard deviation (SD) of the change from baseline to Week 52 in the putamen ipsilateral side SBR will be estimated based on the blinded data using a modified version of Gould-Shih simple adjustment on sample variance (Zucker et al. 1999):

$$s_{adj}^2 = s_{os}^2 - \frac{2N}{9(N-1)} \delta^2,$$

CONFIDENTIAL

The information contained herein may not be used, disclosed, or published without the written consent of Biogen MA Inc.

where N denotes the number of subjects included in the analysis for blinded sample size re-estimation (subjects with both baseline and Week 52 data of the putamen ipsilateral side SBR available at the time of sample size re-estimation), δ is the assumed true treatment effect (same treatment effect assumed for high, medium and low dose group in this analysis), and s_{os}^2 is the unadjusted one sample variance of the estimate of the change from baseline to Week 52 in the putamen ipsilateral side SBR from the pooled blinded data.

The recommendation of sample size increase depends on the comparison of s_{adj}^2 with 0.156, the assumed value of SD for the current sample size (see Section 4). If s_{adj}^2 is less than or equal to 0.156, the value used for sample size calculation when planning the study, the study will continue with the original planned sample size 311. If s_{adj}^2 is greater than 0.156, the study will continue with an increased sample size. The increased sample size will be calculated by using the same MCP-MOD method as specified in Protocol 16.9, subject to a maximum of 413, which is a 30% increase on the original sample size.

7 References

Donald B. Rubin. Inference and missing data. *Biometrika*. 1976;63: 581–592.

Jose Pinheiro, Bjorn Bornkamp, Ekkehard Glimm and Frank Bretz. Model-based dose finding under model uncertainty using general parametric models. *Statistics in Medicine*. 2013;33: 1646–1661.

Stacy M, Hauser R (2007) Development of a Patient Questionnaire to facilitate recognition of motor and non-motor wearing-off in Parkinson's disease. *J Neural Transm* 114:211–217

Christopher G. Goetz, Sheng Luo, Lu Wang, Barbara C. Tilley, Nancy R. LaPelle, Glenn T. Stebbins. Handling Missing Values in the MDS-UPDRS. *Mov Disord*. 2015 October; 30(12): 1632-1638.

